Table of Appendices

APPENDIX 1.	Schedule of Assessments	87
APPENDIX 2.	Study Personnel	90
Appendix 3.1	Investigator Details	90
Appendix 3.2	Sponsor Contact Details	90

List of In-text Tables

Table 3.3.1-1	Epidiolex Adverse Events.....	32
Table 5.1-1	Formulation of GWP42003-P Oral Solution	35
Table 5.2-1	Formulation of Placebo Oral Solution	35
Table 8.1.2-1	Dose Up-Titration Regimen*	42
Table 9.1.9-1	Hematology, Biochemistry, Urinalysis and THC Screen	47

List of In-text Figures

Figure 1-1	Study Design and Treatment Schema	16
Figure 1-2	Study Design and Treatment Schema	17
Figure 9-1	Flow Diagram for Identifying and Evaluating Clinical Trial Adverse Event Data Through Systematic Categorization Tabulation and Analysis which can Illuminate an Abuse Potential Signal.....	55

List of Abbreviations

AE	Adverse Event
AEDs	Antiepileptic Drugs
ALT	Alanine aminotransferase
AST	Aspartate aminotransferase
AUC _(0-∞)	Area under the concentration time curve from zero to infinity with extrapolation of the terminal phase
AUC _(0-t)	The area under the plasma concentration versus time curve, from time zero to 't' (where t = the final time of positive detection) as calculated by the linear trapezoidal method
BP	Blood Pressure
CLB	Clobazam
CBD	Cannabidiol
CI	Confidence Interval
CIOMS	Council for International Organizations of Medical Sciences
CLB	Clobazam
C _{max}	Maximum measured plasma concentration
CRF	Case Report Form
CRO	Contract Research Organization
C-SSRS	Columbia-Suicide Severity Rating Scale
EC	Ethics Committee
ECG	12-lead Electrocardiogram
EU	European Union
GCP	Good Clinical Practice
GW	GW Research Ltd
GWP	GW Pharma Ltd
IB	Investigator Brochure
ICH GCP	International Conference on Harmonization Tripartite Guideline for Good Clinical Practice
IMP	Investigational Medicinal Product
IND	Investigational New Drug
INR	International Normalized Ratio
IRB	Institutional Review Board
ITT	Intention to Treat

IVRS	Interactive Voice Response System
LOCF	Last Observation Carried Forward
MMRM	Mixed-effects Model Repeated Measures
N-CLB	N-desmethylclobazam
OLE	Open label extension
PBPK	Physiologically-based pharmacokinetic interactions
PI	Principal Investigator
PP	Per Protocol
PVD	Pharmacovigilance Department
SAE	Serious Adverse Event
SAP	Statistical Analysis Plan
SUSAR	Suspected Unexpected Serious Adverse Reaction
$t_{1/2}$	Terminal half-life
TBL	Total bilirubin
THC	Δ^9 -tetrahydrocannabinol
t_{max}	Time to the maximum measured plasma concentration
ULN	Upper Limit of Normal
USA	United States of America
VNS	Vagus Nerve Stimulation

Definition of Terms

Term	Definition
Baseline period	The period from screening (Visit 1) to enrollment (Visit 2).
Convulsive seizures	Tonic-clonic, tonic, clonic or atonic seizures.
Countable partial seizures	Partial/focal seizures with a motor or behavioral component that allow such seizures to be easily identified and hence counted.
Day 1	The day a patient is enrolled and begins PK sampling.
End of treatment	Completion of the treatment period (Visit 5 or Visit 12) or withdrawal.
End of study	Last patient's last visit / last contact.
IMP	Investigational Medicinal Product (Study Medication). Used to describe both investigational active product and reference therapy (placebo).
INR	International Normalized Ratio (INR) is a calculation made to standardize prothrombin time.
Investigator	Study Principal Investigator or a formally delegated study physician.
Non-convulsive seizures	Myoclonic, partial or absence seizures.
Partial seizures	Partial (focal) seizures occur when the electrical activity remains in a limited area of the brain.
Status epilepticus	Seizures lasting for 30 minutes or longer.
Sub-types of seizures	Seizure sub-types can be tonic, clonic, tonic-clonic, atonic, myoclonic, absence (typical and atypical), countable partial and other partial.

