13.6.3 Pharmacokinetics

Calculation of PK parameters will be based on actual blood sampling times [h] (relative to the corresponding administration time) rounded to two decimal digits with negative pre-dose times set to zero. Plasma concentrations of CLB, N-CLB, CBD and

the major metabolites will be displayed graphically, summarized and listed. For descriptive statistics, values below the lower limit of quantification of the assay (LLOQ) will be excluded from any calculations. Descriptive statistics of concentrations will be calculated if at least half of the individual data points that have been measured are equal to or above the LLOQ.

For calculation of the PK parameters, the following rules will be applied:

At time zero and at time points in the lag-time between time zero and the first quantifiable concentration, concentrations below the LLOQ will be set to zero. All other concentrations below the LLOQ will not be used in calculations.

Variables derived from plasma concentrations:

- Concentration maximum (C_{\max}): Highest observed plasma concentration of the measured concentration-time profile. Dimension: [amount / volume].
- Terminal half-life $t_{1/2} = \ln(2)/\lambda_z$.
- The rate constant of the terminal phase λ_z will be determined by linear regression of log-transformed concentration data after the time of maximum concentration. A sequence of terminal elimination rate constants will be created by linear regression. Linear regressions are repeated using the last three points with a quantifiable concentration, the last four points, the last five points etc. For each regression, an adjusted R^2 is computed. The regression with the largest adjusted R^2 is selected to estimate the terminal half-life. Dimension: [time].
- Area under the concentration-time curve from administration until the last sampling point (t) equal or above the LLOQ $AUC_{(0-t)}$ will be calculated by the linear trapezoidal formula. Dimension: [time • amount / volume].
- Area under the concentration-time curve extrapolated to infinity: $AUC_{(0-\infty)} = AUC_{(0-t)} + C_{\text{last}}/\lambda_z$ and C_{last} is the concentration observed at the last time point with a quantifiable concentration, λ_z refers to the terminal elimination rate constant. Dimension: [time • amount / volume].
- Time of maximum concentrations: T_{\max} will be taken as the time after administration at which C_{\max} occurs. Dimension: [time].

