9.1.10 Pharmacokinetic Analyses

The plasma concentration/time curves of CLB, N-CLB, CBD, CBD major metabolites, THC and THC major metabolites will be assessed at Visit 2 (Day 1 and Day 2) and Visit 4 (Day 33 and Day 34). Patients will be given their daily dose of clobazam at a scheduled time during Visit 2 and Visit 4 and the GWP42003-P/placebo immediately afterwards (Visit 4 only) to facilitate the accurate timing of blood samples required for PK analysis. Blood samples will be taken by either direct venipuncture or an indwelling cannula inserted into a forearm vein at the following times: Pre-dose and, 15 minutes, 30 minutes, 1 hour, 1.5 hours, 2 hours, 4 hours, 6 hours, 12 hours and 24 hours after dosing. The timing of each PK sample will be relative to the morning dose of CLB.

The pre-dose blood sample will be taken within 30 minutes prior to dosing. The allowable window for post-dose blood sample collection is ± 2 minutes up to and including 1 hour post-dose, ± 5 minutes from 1.5 hours up to and including 6 hours post-dose and ± 1 hour at 12 hours and 24 hours post-dose.

In the event of an AE that, in the opinion of the investigator, is related to a concomitant AED, additional blood samples may be collected.

Analysis of all PK samples will be conducted at a central clinical laboratory. Sample volume requirements and processing procedures will be detailed in a separate laboratory manual.

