9.2.1.2.2 Visit 2 (Day 2) - Enrollment

This is the second part of the two day enrollment visit. The final PK sample will be collected 24 hours after the Day 1 morning CLB dose.

Following completion of the PK sampling process the following observations will be made on Day 2: concomitant medications (including AEDs), physical examination (including body weight), vital signs and AEs.

GWP42003-P/placebo will be dispensed and both the morning dose of CLB and of GWP42003-P/placebo will be taken in clinic. Patients and/or their caregivers will be provided with individual dosing schedules as described in [Section 8.1.2](#). Each patient will then receive their GWP42003-P/placebo for the 10 day titration period followed by the 21 day maintenance period. Patients, or their caregivers, will be instructed on how to record the diary information.

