13.3.2 Pharmacokinetic Analysis Set

All subjects who are treated and receive at least one dose of IMP and who provide some on-treatment data will be included.

The PK analysis set is the primary analysis set for all PK endpoints.

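### AUC(0-t) for clobazam and N-CLB ends at each profile's own last quantifiable sample rather than at a fixed time, so at steady state a missing 24 h sample distorts that patient's exposure ratio

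*Protocol*

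**What the plan says.** AUC(0-t) is among the primary parameters (Protocol Version 2, Section 4.1.1). It is one of three variables whose 90% CI for the ratio of geometric means is compared with [0.5, 2.0] (Version 2 synopsis, Statistical Considerations).

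The List of Abbreviations in Version 2 says that AUC(0-t) runs "from time zero to 't' (where t = the final time of positive detection". Section 13.6.3 defines it as the area "from administration until the last sampling point (t) equal or above the LLOQ", by the linear trapezoidal formula and with actual sampling times. The copy of Version 2 at hand stops before Section 13.6.3, so that wording is taken from Version 1. The Amendment 1 entries for the section change only the analytes and the treatment term.

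On sampling, Section 9.2.1.2.2 says "The final PK sample will be collected 24 hours after the Day 1 morning CLB dose", and Visit 4 has the matching sample on Day 34. Section 9.1.10 sets the window at ± "1 hour at 12 hours and 24 hours post-dose". Section 13.3.2 admits to the PK set all treated subjects who "receive at least one dose of IMP and who provide some on-treatment data will be included". The text at hand defines no AUC over 0-24 h or over a dosing interval.

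**The concern.** Ending an area at the last quantifiable concentration suits a single dose that decays towards zero, where the missing tail is small. That is not the situation here. CLB must be stable from four weeks before screening (Section 6.1.6), and the rationale of Amendment 1 says that CLB takes up to 14 days to reach steady state. Both profiles are therefore steady-state profiles that are still well above zero at 24 h.

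Under these conditions AUC(0-t) depends heavily on t. If t differs between Day 1 and Day 33, the ratio mixes interval length with exposure. A Day 33 profile that stops early pulls the ratio down and can hide an increase. A Day 1 profile that stops early pushes it up and can suggest one.

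**Working it through.** The protocol states no figure for this quantity, so there is none to reproduce.

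**Inputs from the documents.** Samples at 0, 0.25, 0.5, 1, 1.5, 2, 4, 6, 12 and 24 h; ±1 h window on the last two; linear trapezoid at actual times; 20 patients at 4:1, so 20 × 4/5 = 16 on GWP42003-P; 90% CI against [0.5, 2.0].

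**Assumptions (not in the documents).** One-compartment oral profile at steady state, absorption rate 1.5/h, half-life 12 to 100 h, CLB once or twice daily, next morning dose held until after the last sample. SD of the log ratio 0.2 to 0.4. Sixteen paired log ratios, t with 15 df.

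**Step 1: one profile ends at 12 h, the other at 24 h, no interaction.** For a flat profile the area is proportional to t, so the false ratio is 24/12 = 2.00 (or 0.50, depending on the day). For modelled profiles:

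| Half-life (h) | 12 | 24 | 36 | 72 | 100 |
|---|---|---|---|---|---|
| CLB once daily | 1.55 | 1.74 | 1.82 | 1.90 | 1.93 |
| CLB twice daily | 1.72 | 1.85 | 1.90 | 1.95 | 1.96 |

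**Step 2: sampling window only.** The extreme case is 25 h on one day and 23 h on the other. For a flat profile this gives 25/23 = 1.087, and modelled profiles give 1.05 to 1.08. If times are uniform within ±1 h on each day, the SD of t is 1/√3 = 0.577 h, and the added SD of the log ratio is √2 × 0.577/24 = 0.034. An SD of 0.20 becomes √(0.20² + 0.034²) = 0.203.

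**Step 3: effect on the tested ratio.** If k of 16 pairs are wrong by a factor of 2 in the same direction, the geometric mean ratio is multiplied by 2^(k/16) or 2^(-k/16):

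- k = 1: 1.044 or 0.958
- k = 2: 1.091 or 0.917
- k = 4: 1.189 or 0.841
- k = 16: 2.00 or 0.50

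With a true ratio of 1 and SD 0.3, the 90% CI is 0.88-1.14 with no truncation. It becomes 0.90-1.22 with one Day 1 profile truncated and 0.98-1.44 with four. All lie inside [0.5, 2.0].

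**Step 4: when the conclusion could change.** The variance of the log ratio with k truncated pairs is SD² + (ln 2)² × p(1-p) × 16/15, where p = k/16. The upper limit is the true ratio times a factor. Dividing 2.0 by that factor gives the largest true ratio for which no meaningful effect would be declared, taking the estimate at its expected value:

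| Profiles ending at 12 h | SD 0.2 | SD 0.4 |
|---|---|---|
| None | 2/1.092 = 1.83 | 2/1.192 = 1.68 |
| One, Day 33 | 2/1.075 = 1.86 | 2/1.159 = 1.73 |
| Two, Day 33 | 2/1.050 = 1.90 | 2/1.124 = 1.78 |
| One, Day 1 | 2/1.173 = 1.71 | 2/1.264 = 1.58 |
| Two, Day 1 | 2/1.249 = 1.60 | 2/1.337 = 1.50 |

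For example, with SD 0.2 a true ratio of 1.88 has an upper limit of 1.88 × 1.092 = 2.05, so no declaration follows. With two Day 33 profiles cut at 12 h the limit is 1.88 × 1.050 = 1.97, and lack of effect would be declared. The lower boundary mirrors this.

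**The case against.** The strongest reply is that the planned profiles already give the right quantity. At steady state the 24 h level is comparable with the pre-dose level, so the last quantifiable sample will be the 24 h sample and AUC(0-t) is AUC(0-24). Only a missed, lost or unusable sample shortens the interval. This stands, and it limits how often the problem can arise; the documents give no rate of sample loss.

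A reader might infer that Visit 2 is the weak point because patients may go home and return on Day 2. The documents do not support this. Section 9.2.1.2.2 places the 24 h sample before dispensing and the first dose in clinic, so a patient who fails to return does not start treatment and has no Day 33 profile to pair. At Visit 4 the last sample likewise precedes the Day 34 dispensing.

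A reader might also infer that the tested CLB or N-CLB ratio could be wrong by two-fold, or that a late sample could do this. Neither holds. Two-fold is one patient's ratio, whereas the rule applies to the CI of the geometric mean ratio, and all 16 patients would have to be truncated on the same day to move that by two-fold. An off-time sample within the window cannot exceed about 9% in one patient and averages out.

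Finally, rules for incomplete profiles often sit in the SAP. Section 13.3.3 foresees exclusions, and Section 13.3.2 defines who is in the set, not which areas are compared. An SAP may well add such a rule. The point here is narrower: the protocol itself fixes where the area ends, and that choice does not suit steady-state profiles.

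**Conclusion.** The point holds as a modest defect in the stated definition of a primary parameter. A pair in which one profile lacks a usable 24 h sample and ends at 12 h gives a false patient-level ratio of about 1.5- to 2-fold. One such pair in 16 shifts the geometric mean ratio by about 4%, and two shift it by about 8-9%. The timing window is a minor source of noise.

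If the true ratio is near 1, no plausible number of lost samples changes the conclusion. Near a boundary, one or two can: in the worked cases, for true ratios between about 1.5 and 1.9, depending on which day is truncated and on the SD.

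These sizes rest on the assumed half-lives, log-ratio SD and paired analysis of 16 patients. They also rest on Section 13.6.3 carrying over into Version 2 unchanged apart from the logged amendments.

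**What to change.** For CLB and N-CLB, use in the ratio model an AUC over the same fixed interval on both days: 0-24 h, or the patient's CLB dosing interval. Interpolate or extrapolate to the nominal end time when the last sample is early or late. If either day lacks a usable end-of-interval sample, leave that pair out of the primary AUC ratio and compare both days over the longest common interval (0-12 h) as a sensitivity analysis. Keep AUC(0-t) as a descriptive parameter. With no interaction, the interval-length error is then removed by construction.

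The cost is wording in Section 13.6.3 and in the list of PK parameters, plus a partial-area calculation that is standard in PK software. No samples, visits or patients are added. The small downside is that a patient with an incomplete profile leaves the primary AUC ratio.

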2. OBJECTIVES

2.1 Primary

To determine whether GWP42003-P affects the pharmacokinetic (PK) profile of clobazam (CLB) and its primary metabolite N-desmethylclobazam (N-CLB).

2.2 Secondary

To assess the safety and tolerability of GWP42003-P in the presence of CLB.

3. BACKGROUND AND RATIONALE

3.1 Disease

Epilepsy is a common disorder¹. Approximately 1% of the world's population is chronically affected by epilepsy². It shows no particular geographic distribution and the gender distribution is more or less equal. The incidence of epilepsy is greater in childhood and in elderly people^{2,3,4,5}. Focal seizures represent the most frequent seizure type (around 60% of all cases of epilepsy, and a substantial percentage of them are not well controlled)⁶.

Overall, and despite the introduction of a substantial number of new antiepileptic drugs (AEDs) in the last two decades, around 30% of patients remain refractory to currently available treatment^{7,8,9}. In addition, most currently approved AEDs are associated with significant motor and cognitive adverse reactions^{10,11}.

Currently available AEDs each belong to one of a large number of different classes. The principal targets for existing AEDs tend to be either modulators of voltage-dependent ion channels, enhancers of inhibitory neurotransmission, and attenuators of excitatory neurotransmission, with the aim being to reduce neuronal excitotoxicity^{12,13}.

3.2 GWP42003-P Background

The cannabis plant (*Cannabis sativa* L.) produce trichomes that synthesize a large number of pharmacologically active compounds called phytocannabinoids. The most abundant of these are Δ^9 -tetrahydrocannabinol (THC) and cannabidiol (CBD), although the amounts and proportions of the various phytocannabinoids in each plant vary by strain and can be adjusted by breeding.

The Investigational Medicinal Product (IMP), GWP42003-P, is formulated from extracts prepared from *Cannabis sativa* L. plants that have a defined chemical profile and contain consistent levels of CBD as the principal phytocannabinoid. Extracts from

these plants are processed to yield pure (>98%) CBD that typically contains less than 0.5% (w/w) THC. The pure CBD is subsequently dissolved in excipients with added sweetener and flavoring.

The pharmacological effects of phytocannabinoids are thought to be mediated primarily via their interaction with the endocannabinoid system, which consists of cannabinoid receptors, endogenous ligands (endocannabinoids) and enzymes for endocannabinoid synthesis and degradation. Two G-protein-coupled receptors for cannabinoids have so far been identified, designated cannabinoid CB₁ and CB₂ receptors. CBD does not bind to either of these receptors with any great affinity but does modulate the metabolizing enzymes of the endocannabinoid system. CBD also affects ion channel conductance and acts on other G-protein-coupled receptors such as the transient receptor potential channel TRPV1¹⁴ and the orphan receptor GPR55¹⁵. Importantly, in contrast to THC, CBD lacks detectable psychoactivity. CBD has demonstrated anticonvulsant, antipsychotic, anxiolytic, neuroprotective, antioxidant and anti-inflammatory activity¹⁶. Very little data concerning AEs of CBD in humans exists to date. However, doses of up to 1500 mg CBD per day are reported to be well tolerated in humans¹⁷.

3.3 Rationale

CBD has shown therapeutic potential as an AED, with preclinical studies demonstrating anticonvulsant effects in a number of animal models of seizure^{16,18,19}. Although no placebo-controlled trials have been completed to date, a recent parent survey has reported that 84% of children with treatment-resistant epilepsy experienced a reduction in seizures while taking CBD-enriched cannabis, with over half of those reporting either >80% reduction in seizure frequency or complete seizure freedom²⁰. The CBD-enriched cannabis was behaviorally well tolerated and children often experienced improved sleep, increased alertness and better mood. There has been a program of expanded access by GW Pharma Ltd (GWP) in the USA, primarily in children with severe epilepsy, that has shown encouraging reports of reductions in multiple seizure types with good tolerability in 151 exposures²¹.

Population-based studies of drug utilization demonstrate that 19-24% of patients with epilepsy use polytherapy with AEDs^{22,23,24}. In recent studies of children and adults with refractory epilepsy, 64 % used polytherapy with two or more AEDs, resulting in a considerable risk of interactions^{25,26}. CLB is a widely used AED, prescribed with other medication(s) to control seizures in adults and children two years of age and older who have Lennox-Gastaut syndrome (a disorder that causes seizures and often

developmental delays). The pharmacological action of CLB is to decrease abnormal electrical activity in the brain via allosteric activation of the ligand-gated γ -aminobutyric acid (A) receptor.

CLB is in a class of medications called benzodiazepines. Similar to other benzodiazepine medications, clobazam is metabolized by cytochrome P450 (CYP450) enzymes (mainly in the liver). This metabolism results in the formation of an active metabolite N-CLB, amongst others.

Cytochrome P450 enzymes are a family of heme-containing enzymes responsible for the metabolism of over half of all prescribed medications and interactions with these enzymes are the major source of physiologically-based pharmacokinetic (PBPK) interactions between drugs. It is anticipated that patients taking GWP42003-P may also be taking clobazam and as CBD has been shown to both inhibit CYP450 enzymes in vitro (K_i CYP3A4 = 1.5 μ M) and induce CYP450 enzymes in vitro (EC_{50} CYP3A4 = 1.2 μ g/mL) a possibility of a pharmacokinetic (PK) interaction between CBD and clobazam exists. Furthermore, CLB has been shown to undergo PBPK interactions with other AED medications via both CYP induction (such as with felbamate where the formation of the active metabolite of clobazam, N-CLB was increased several-fold²⁷) and also CYP inhibition (such as with stiripentol where serum concentrations of CLB were increased and metabolites decreased^{28,29,30}).

Given the high likelihood that patients prescribed CBD will also be using clobazam, it is the aim and purpose of this study to determine whether a PK interaction between CBD and CLB exists.

3.3.1 Selection of Study Doses

Doses up to 800 mg GWP42003-P per day for up to eight weeks have been well tolerated in adults in GW Research Ltd (GW) clinical study GWMD09112, which, assuming an average weight of 70 kg, equates to a daily dose of 11.4 mg/kg. In the literature, doses of GWP42003-P have been given up to 1500 mg GWP42003-P per day for four weeks in adults, which, in a 70 kg human equates to a daily dose of 21.4 mg/kg GWP42003-P.

Data on the safety of GWP42003-P is emerging from the physician-initiated Epidiolex[®] Expanded Access Program being conducted in the USA. This program has been running since January 2014 and at the time of writing had data on 63 patients. The mean maximum exposure achieved in this patient population of refractory epilepsies was a daily dose of 24.4 mg/kg (n=59 patients) with a maximum dose of 51 mg/kg in one patient. Please see below for a break-down of the groups:

- ≤ 20 mg/kg GWP42003-P n=13 (21%)

- >20 mg/kg - ≤30 mg/kg GWP42003-P n=40 (64%)
- >30 mg/kg - ≤40 mg/kg GWP42003-P n=4 (6%)
- >40 mg/kg GWP42003-P n=2 (3%)
- Dose not reported n=4(6%)

Eleven patients had a daily GWP42003-P dose of >25 mg/kg, of which five did not report any adverse events (AEs). Of note, the patient who received 51 mg/kg did not have any AEs at this dose. The remaining six patients experienced AEs as documented in the [Table 3.3.1-1](#) below:

Table 3.3.1-1 Epidiolex Adverse Events	
Adverse Event Term	Number of Events
Loose stools / urgent bowel movements	2
Increase in seizures	2
Drowsiness	1
Aspiration pneumonia	1
Lethargy	1
Decreased appetite	1
Dyskinesia	1
Urinary tract infection	1

Based on the above, a daily dose up to 20 mg/kg/day (given as two divided doses) has been selected for the GWP42003-P dose in the current study, including a titration period with daily increments of 2.5 mg/kg and 5 mg/kg. At the end of the treatment period, patients will be given the option of continuing onto an open label extension (OLE) period if the investigator and patient both agree that it is in their best interest. During the OLE doses may be adjusted up or down, dependent on investigator opinion, to a maximum daily dose of 30 mg/kg GWP42003-P.

